5.5.1.1. Liver Chemistry Stopping Criteria, Participant Management and Follow-Up

Participants who develop ALT $\geq 5 \times \text{ULN}$ must be followed weekly until resolution or stabilization (ALT $< 5 \times \text{ULN}$ on 2 consecutive evaluations).

When any of the liver chemistry stopping criteria is met, do the following:

- Immediately hold IP. If on LA therapy, **do not** administer another injection until approval is received from the ViiV Safety and Labelling Committee.
- Report the event to the Medical Monitor within 24 hours of learning its occurrence.
- Complete the liver event eCRF and SAE eCRF, where applicable.
- Complete the liver imaging and/or liver biopsy eCRFs if these tests are performed.
- Perform liver event follow up assessments (described below), and monitor the participant until liver chemistries resolve, stabilize, or return to Baseline values as described below.
- Make every reasonable attempt to have participants return to clinic within 24 hours for repeat liver chemistries, liver event follow-up assessments (see below), and close monitoring.
- A specialist or hepatology consultation is recommended.
- Monitor participants twice weekly until liver chemistries (ALT, AST, alkaline phosphatase, bilirubin) resolve, stabilize or return to within Baseline values.

Make every attempt to carry out the **liver event follow-up assessments** described below:

- Viral hepatitis serology including:
 - Hepatitis A immunoglobulin M (IgM) antibody;
 - Hepatitis B surface antigen (HBsAg) and Hepatitis B Core Antibody (IgM);
 - Hepatitis C RNA;
 - Hepatitis E IgM antibody;
 - Cytomegalovirus IgM antibody;
 - Epstein-Barr viral capsid antigen IgM antibody (or if unavailable, obtain heterophile antibody or monospot testing);
- Syphilis screening;
- Drugs of abuse screen including alcohol;
- Serum acetaminophen test (N-acetyl-para-aminophenol [APAP] adduct test). The site must contact GSK when this test is required. Please refer to the central laboratory manual.
- Blood sample for pharmacokinetic (PK) analysis, obtained during follow up assessments. Record the date/time of the PK blood sample draw and the date/time of

the last dose of investigational product prior to blood sample draw on the eCRF. If the date or time of the last dose is unclear, provide the participant's best approximation. If the date/time of the last dose cannot be approximated OR a PK sample cannot be collected in the time period indicated above, do not obtain a PK sample. Instructions for sample handling and shipping are in the SPM.

- Serum creatine phosphokinase (CPK) and lactate dehydrogenase (LDH);
- Fractionated bilirubin, if total bilirubin is greater than 1.5xULN;
- Obtain complete blood count with differential to assess eosinophilia;
- Anti-nuclear antibody, anti-smooth muscle antibody, and Type 1 anti-liver kidney microsomal antibodies, and quantitative total immunoglobulin G (IgG or gamma globulins);
- Liver imaging (ultrasound, magnetic resonance, or computerized tomography) and/or liver biopsy to evaluate liver disease; complete Liver Imaging and/or Liver Biopsy CRF forms.
- Record the appearance or worsening of clinical symptoms of hepatitis, or hypersensitivity, fatigue, decreased appetite, nausea, vomiting, abdominal pain, jaundice, fever, or rash as relevant on the AE report form;
- Record use of concomitant medications, acetaminophen, herbal remedies, other over the counter medications, or putative hepatotoxins, on the concomitant medications report form. Record alcohol use on the liver event alcohol intake case report form.

5.5.1.2. Liver Event Adjudication Committee

A liver safety panel will be used to evaluate all participants who meet liver stopping criteria. Uniform sets of data and standards for adjudication will be applied across cases to inform outcomes. Full details of the analysis, timing, and the decision criteria will be pre-specified in an Adjudication Committee Charter.

5.5.1.3. Liver Chemistry Stopping Criteria – Restart / Rechallenge

Participants who meet liver toxicity stopping criteria should not be retreated with investigational product unless an exemption has been approved by the ViiV Safety and Labeling Committee (VSLC). The guideline for Restart /Rechallenge approved by the VSLC, which is maintained as a separate document must be followed.

5.5.1.3.1. Drug Restart / Rechallenge. Following Liver Events that are Possibly Related to IP

- Approval by the VSLC for drug restart or additional IM administration can be considered where:
- The participant is receiving compelling benefit, benefit of drug restart exceeds risk, and no effective alternative therapy is available. Ethics Committee or Institutional Review Board approval of drug restart / rechallenge must be obtained, as required.

- If the restart / rechallenge is approved by the VSLC in writing, the participant must be provided with a clear description of the possible benefits and risks of drug administration, including the possibility of recurrent, more severe liver injury or death.
- The participant must also provide signed informed consent specifically for the IP restart / rechallenge. Documentation of informed consent must be recorded in the study chart.
- Study drug must be administered at the dose specified by the VSLC.
- Participants approved by the VSLC for rechallenge of IP must return to the clinic twice a week for liver chemistry tests for a minimum of one month and thereafter for as long as clinically indicated and then laboratory monitoring may resume as per protocol. If protocol defined stopping criteria for liver chemistry elevations are met, study drug must be stopped.

5.5.1.3.2. Drug Restart Following Transient Resolving Liver Events Not Related to IP

Approval by the VSLC for drug restart or additional IM administration can be considered where:

- Liver chemistries have a clear underlying cause (e.g., biliary obstruction, hypotension and liver chemistries have improved to normal or are within 1.5 x baseline and ALT <3xULN). Ethics Committee or Institutional Review Board approval of drug restart/rechallenge must be obtained, as required.
- If restart / redosing of drug is approved by the VSLC in writing, the participant must be provided with a clear description of the possible benefits and risks of drug administration, including the possibility of recurrent, more severe liver injury or death.
- The participant must also provide signed informed consent specifically for the restart. Documentation of informed consent must be recorded in the study chart.
- Study drug must be administered at the dose specified by the VSLC.

Participants approved by the VSLC for restarting or re-dosing IP must return to the clinic once a week for liver chemistry tests for a minimum of one month and thereafter for as long as clinically indicated and then laboratory monitoring may resume as per protocol. If protocol defined stopping criteria for liver chemistry elevations are met, study drug must be stopped.

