7.4.5.6. Lipase Elevations and Pancreatitis

Participants with asymptomatic Grade 1 or 2 elevations in lipase may be followed closely for the development of symptoms.

Participants with asymptomatic Grade ≥ 3 elevations in lipase that are considered possibly or probably related to IP should have IP interrupted until serum lipase returns to Grade ≤ 2 . The lipase assay should be repeated within 2 weeks of any Grade ≥ 3 result. Participants with persistence of Grade ≥ 3 lipase in the absence of other diagnoses or reoccurrence of lipase elevation (at Grade ≥ 2) following reintroduction of IP should permanently discontinue IP.

Participants with a confirmed diagnosis of clinical pancreatitis that is considered possibly or probably related to IP should have IP held. After complete resolution of the episode, participants may be re-challenged with IP after discussion with the Medical Monitor, only if the Investigator has compelling evidence that the event was not caused by IP. Upon re-challenge, lipase determinations should be performed every 2 weeks for at least 6 weeks after re-initiation of treatment. With any elevation of lipase of Grade ≥ 2 or any recurrence of symptoms, the participant should discontinue IP and be withdrawn from study.

Any participant receiving at least one dose of CAB LA and /or RPV LA who discontinue IP / Withdraw will initiate treatment with HAART and enter the LTFU Phase for 52 weeks of **follow up**.

Drug Restart Following Transient Resolving Liver Events Not Related to Study Drug

Approval by VSLC for drug restart can be considered where:

Liver chemistries have a clear underlying cause (e.g., biliary obstruction, hypotension, and liver chemistries have improved to normal or are within $1.5 \times$ baseline and $ALT < 3 \times ULN$). Ethics Committee or IRB approval of drug restart must be obtained, as required.

If restart of drug is approved by VSLC in writing, the participant must be provided with a clear description of the possible benefits and risks of drug administration, including the possibility of recurrent, more severe liver injury or death.

The participant must also provide signed informed consent specifically for the restart. Documentation of informed consent must be recorded in the study chart.

Study drug must be administered at the dose specified by VSLC.

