Participants approved by VSLC for restarting study drug must return to the clinic once a week for liver chemistry tests for a minimum of one month and thereafter for as long as clinically indicated and then laboratory monitoring may resume as per protocol. If protocol defined stopping criteria for liver chemistry elevations are met, study drug must be stopped.

Refer to Section 11.2, U.S. Department of Health and Human Services, National Institutes of Health, National Institute of Allergy and Infectious Diseases, Division of AIDS. Division of AIDS (DAIDS) Table for Grading the Severity of Adult and Pediatric Adverse Events, Version 2.1. [March 2017]. Available from: <https://rsc.tech-res.com/docs/default-source/safety/daids-ae-grading-table-mar2017.pdf>

Refer to Section 11.3, Appendix 3: Liver Safety – Study Treatment Restart Guidelines for further details.

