11.3.3. VSLC Decision Process for Drug Restart Approval or Disapproval

- Principal Investigator (PI) requests consideration of drug re-initiation for a participant stable or improving on IP, who exhibits liver chemistry elevation meeting participant stopping criteria, which is transient, non-drug-related, and liver chemistries have improved to normal or are within 1.5x baseline and ALT < 5xULN.
- GSK Medical Monitor and GCSP Physician to review the participant's diagnosis restart risk factors (Hepatotoxicity Panel consultation is available) and complete checklist (Table 13).
 - *must present source data defining the patient's current resistance profile with documented evidence of extensive drug resistance and previous drug history.*
- The local operating company (LOC) medical director should be informed that study drug restart is under consideration and of the final decision, whether or not to proceed.
- Relevant physicians (listed below) must review and agree on action to be taken regarding request for drug restart:
- Safety Review Team Leader, Safety Development Leader, or Senior Safety Physician
- MDL and PPL
- Request is taken to VSLC for final decision

Table 13 Checklist for Phase III drug restart after well-explained liver injury (e.g. biliary, pancreatic, hypotensive events, congestive heart failure (CHF), acute viral hepatitis), and improvement of liver chemistry to normal or $\leq 1.5x$ baseline & ALT < 5xULN

	Yes	No
Is participant stable or improving on IP?		
Do not restart if the following risk factors at initial liver injury:		
fever, rash, eosinophilia, or hypersensitivity		
drug-induced liver injury		
alcoholic hepatitis (AST > ALT, typically < 10xULN)		
IP has an HLA genetic marker associated with liver injury (e.g. lapatinib, abacavir, amoxicillin/clavulanate)		
Source data defining the patients current resistance profile		
Previous drug history		

Figure 18 VSLC process for drug restart approval or disapproval

11.3.4. Medical monitor, GCSP Physician and PI actions for Restart or Rechallenge following VSLC decision

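### The ALT ceiling for considering drug restart after a liver event not related to study drug is <3xULN in the protocol body but <5xULN in Appendix 3, with no order of precedence

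*Protocol*

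**What the plan says.** Four places in the current protocol text state the condition for a restart after a liver event with a clear cause other than study drug.

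- **Section 5.5.1.3.2:** "liver chemistries have improved to normal or are within 1.5 x baseline and ALT <3xULN".
- **Section 7.4.5.6** (placed after the lipase and pancreatitis text): introduced by "Approval by VSLC for drug restart can be considered where", it continues "Liver chemistries have a clear underlying cause (e.g., biliary obstruction, hypotension, and liver chemistries have improved to normal or are within" 1.5 times baseline, and ends with the same <3xULN ceiling.
- **Appendix 3, section 11.3.3:** "liver chemistries have improved to normal or are within 1.5x baseline and ALT < 5xULN".
- **Appendix 3, Table 13** (the restart checklist): the title asks for "improvement of liver chemistry to normal or" at most 1.5 times "baseline & ALT < 5xULN".

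Two pointers connect these texts. The passage under 7.4.5.6 closes with "Refer to Section 11.3, Appendix 3: Liver Safety", offered as further detail. Section 5.5.1.3 adds: "The guideline for Restart /Rechallenge approved by the VSLC, which is maintained as a separate document must be followed". Neither pointer gives an ALT figure or says which text governs if they differ.

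Section 11.3.3 and Table 13 also ask for source data on the participant's resistance profile and drug history. Sections 5.5.1.3.2 and 7.4.5.6 do not mention this.

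**The concern.** All four places concern the same committee, the same type of event and the same decision, and they share the same condition relative to baseline. Only the absolute ALT ceiling differs. A reader who starts in the body finds one limit, follows the pointer to Appendix 3 and finds another.

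At stake is whether a request may be put forward and considered at all. Under 11.3.3 a request at, say, 3.5xULN can qualify. Under 5.5.1.3.2 the same request does not meet the condition for consideration. Section 5.5.1.2 promises uniform data and standards when liver cases are adjudicated, and two ceilings work against that.

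The decision carries weight because 5.5.1.3.2 covers further intramuscular dosing as well as oral restart, and section 6.9.1 notes that both long-acting drugs may be measurable in plasma for more than a year after injection.

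**Working it through.** No sample size, power or error-rate figure is involved. The check is a comparison of the texts, followed by arithmetic on where they part.

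**Side by side**

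| Place | Relative condition | Absolute ALT ceiling |
|---|---|---|
| 5.5.1.3.2 | normal, or within 1.5 x baseline | <3xULN |
| 7.4.5.6 (restart text) | normal, or within 1.5 x baseline | <3xULN |
| 11.3.3 | normal, or within 1.5 x baseline | <5xULN |
| Table 13 title | normal, or at most 1.5 x baseline | <5xULN |

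**Where the two rules give different answers.** Write A for current ALT and B for baseline ALT, both in multiples of ULN. A participant whose ALT is back to normal meets both rules. Otherwise:

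- Body rule met: A ≤ 1.5B and A < 3.
- Appendix rule met: A ≤ 1.5B and A < 5.
- They disagree when 3 ≤ A < 5 and A ≤ 1.5B.

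**Lowest baseline at which this can happen.** A ≥ 3 and A ≤ 1.5B together require 1.5B ≥ 3, so B ≥ 3/1.5 = 2. Below a baseline of 2xULN the difference in ceilings has no effect.

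**Highest ALT that can be affected.** Exclusion criterion 33 bars ALT of 3xULN or more at screening. Assuming baseline is also below 3xULN, A ≤ 1.5B < 1.5 x 3 = 4.5. The reachable band is therefore 3xULN to <4.5xULN. Reaching the whole range up to 5xULN would need a baseline of at least 5/1.5 = 3.33xULN, which is above the screening limit.

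| Baseline (xULN) | 1.5 x baseline | ALT range in dispute (xULN) |
|---|---|---|
| 1.0 | 1.5 | none |
| 1.9 | 2.85 | none |
| 2.0 | 3.0 | 3.0 only |
| 2.5 | 3.75 | 3.0 to 3.75 |
| 2.9 | 4.35 | 3.0 to 4.35 |
| approaching 3.0 | approaching 4.5 | 3.0 to <4.5 |

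**Example.** Baseline 2.5xULN, current ALT 3.5xULN. The ratio is 3.5/2.5 = 1.4, so the relative condition is met. The body rule fails (3.5 is not below 3) and the appendix rule is met (3.5 is below 5).

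**Can such participants be enrolled?** Yes. Criterion 33 admits ALT from 2 to <3xULN, and criterion 20 allows hepatitis C co-infection under conditions. The protocol gives no count of participants expected in that range.

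**The case against.** The strongest reply is that the mismatch changes little in practice. Neither text grants a restart. Section 5.5.1.1 bars another injection until the VSLC approves, 5.5.1.3 rules out retreatment without its exemption, and 11.3.3 routes each request through the Medical Monitor, the safety physician and named senior physicians to the VSLC for the final decision. Specific consent and weekly liver tests follow any approval. Section 7.4.4.2 separately requires consultation with the Medical Monitor before injections begin or continue in anyone with ALT of 3xULN or more, which covers the whole disputed band. The separate guideline may also settle the figure. All of this stands as a limit on consequence. It does not remove the conflict: the condition for consideration still has two values, and the guideline is not reproduced, so its figure is unknown.

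Three stronger readings are tempting but not supported.

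- **Every participant with ALT from 3 to <5xULN is treated in opposite ways.** The shared 1.5-times-baseline condition removes most of that range for most participants, and the ceiling decides only whether a restart may be considered, not who is dosed.
- **The investigator and the committee would each apply a different limit.** The investigator requests and the VSLC decides. Both texts describe that one decision, so the realistic effect is uncertainty over which requests to submit or consider.
- **The resistance source-data item is a second contradiction.** It appears only in Appendix 3, to which the body refers for further detail. An added documentation step supplements the body and conflicts with nothing stated there. Its scope is still worth a question: the same requirement stands in 11.3.2 for rechallenge, it speaks of extensive drug resistance, and criterion 29 excludes participants with known major integrase or NNRTI mutations other than K103N.

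**Conclusion.** The point holds as an internal inconsistency in current operative text: <3xULN in two body places, <5xULN in two Appendix 3 places, for the same VSLC restart decision and with no order of precedence. It is confined to restarts after events not related to study drug. Rechallenge after drug-induced injury, the liver stopping criteria and the efficacy analysis are untouched.

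The affected group is narrow. It needs a baseline ALT of at least 2xULN and a current ALT of at least 3xULN that is still within 1.5 times baseline. The upper end of 4.5xULN rests on the assumption that Day 1 baseline, like screening ALT, is below 3xULN; a higher Day 1 value would widen the band towards 5xULN. Because the group is small and the committee must approve every case, the severity is moderate. It still needs correcting, since a safety threshold should have one value. No view is taken here on which ceiling is right.

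**What to change.** Reconcile sections 5.5.1.3.2, 7.4.5.6, 11.3.3 and the Table 13 title to a single ALT ceiling, and check that it agrees with the separately maintained VSLC guideline cited in 5.5.1.3. State which text governs if they ever differ. The value is for the sponsor's hepatic safety group to set.

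At the same time, the sponsor should confirm whether the resistance source-data requirement in 11.3.3 and Table 13 is meant for restarts as well as rechallenges, and word the body and appendix accordingly.

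The cost is a wording correction in the next amendment and in the committee's checklist. No visit, sample or analysis changes.

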5.5.2. QTc Stopping Criteria

A participant who has a QTc interval >550 msec considered causally related to IP will be withdrawn from the study. The QTc should be based on averaged QTc values of triplicate electrocardiograms obtained over a brief (e.g., 5 to 10 minute) recording period.

If an alternative cause of the QT prolongation is determined (e.g., participant receiving drug known to cause prolonged QT or TdP), the IP may be restarted (or continued) after

consultation and agreement with the Medical Monitor. RPV and RPV LA should not be administered to patients who are receiving a drug known to be associated with TdP.

When performing ECGs, the *same* QT correction formula *must* be used for *each individual participant* to determine eligibility for, and discontinuation from, the study. This formula may not be changed or substituted once the participant has been enrolled.

For example, if a participant is eligible for the protocol based on QTcB, then QTcB must be used for discontinuation of this individual participant as well.

Once the QT correction formula has been chosen for a participant's eligibility, the *same formula* must continue to be used for that participant *for all QTc data being collected for data analysis*. Safety ECGs and other non-protocol specified ECGs are an exception.

5.5.3. Virologic Failure

Only plasma HIV-1 RNA values determined by the central laboratory will be used to assess virologic failure.

5.5.4. Definition of Protocol-Defined Confirmed Virologic Failure

For the purposes of clinical management in this study, CVF is defined as:

Rebound as indicated by two consecutive plasma HIV-1 RNA levels ≥ 200 c/mL after prior suppression to < 200 c/mL.

5.5.5. Managing Virologic Failure

Following study entry, no changes, or intensification of ART will be permitted prior to protocol-defined virologic failure, outside of the planned protocol regimens. Only plasma HIV-1 RNA values determined by the central laboratory will be used to assess virologic failure. Baseline plasma HIV-1 RNA is the assessment completed on study Day 1. The definition of confirmed virologic failure does not apply to participants in the LTFU Phase. These participants will be followed for the emergence of viral resistance.

Inadequate adherence is a common cause for virologic failure, and should be explored as a first step in the management of study participants (e.g., at the first indication of inadequate virologic response or rebound). Upon notification that a participant's HIV-1 RNA plasma level qualifies him/her as a suspected virologic failure, the Investigator should query the participant regarding intercurrent illness, recent immunization, or interruption of oral therapy.

5.5.5.1. HIV-1 RNA Blips

HIV-1 RNA "blips" are not usually associated with subsequent virologic failure [DHHS, 2016]. Although the implications of persistent HIV-1 RNA levels between the lower level of detection and < 200 c/mL are unclear, the risk of emerging resistance is believed to be relatively low.

Participants with transient increases in HIV-1 RNA ('blips' HIV-1 RNA <200 c/mL) are not considered suspected virologic failures and do not require a change in therapy.

Participants who have a HIV-1 RNA ≥ 50 c/mL and <200 c/mL at the key analysis timepoints (Week 48 and Week 96) must return to the clinic as soon as possible (but no later than 4 weeks after the date of the Week 48 and 96 visit, respectively) for a repeat HIV-1 RNA test such that the result falls within the same analysis window.

In order to better characterize HIV-1 RNA 'blips,' if there is a known reason / explanation for the blip (e.g., immunization, allergies, etc.), the study team should be notified of the reason and case context.

If the Investigator has concerns regarding persistent low level viremia (HIV-1 RNA ≥ 50 c/mL and <200 c/mL), the Medical Monitor should be contacted to discuss participant management. Following discussion with the Medical Monitor, additional viral load testing may be performed between visits to determine the appropriate participant disposition for the next scheduled visit

